XR-NTX is a suspension containing naltrexone embedded in material comparable to surgical sutures. Following injection the normal metabolic process gradually erodes the suspension material and releases naltrexone continuously. Plasma concentrations of naltrexone and 6-beta naltrexol (the main metabolite) are detectable for at least 30 days after a single injection, and the medication must be re-administered to maintain its' effect. Continued use is not associated with tolerance or withdrawal, but naltrexone will precipitate withdrawal if given to a person who is physiologically dependent on opioids thus patients must be detoxified prior to dosing. There is a transient peak of naltrexone about two hours after injection followed by a second peak 2-3 days later that reaches approximately 25 ng/ml followed by a decline to about 12 ng/ml to day 7 with a more gradual reduction that reaches 1-2 ng/ml in 30 days. The once/month injection reduces first pass metabolism to 6-beta-naltrexol that occurs after the oral formulation, thus allowing for less total drug to be administered than the oral, though total naltrexone exposure is 3-4 times higher over 28 days than with a 28-day course of the 50 mg/day oral dose.

[figure not shown]
Study Duration: Three Years

Subject Duration: Six months

Estimated Time to Complete Enrollment: 2019

STUDY SCHEMATIC

STUDY FLOW TABLE

Windows for assessments:
Baseline = 14 days; weekly = ± 2 days; monthly = ± 1 week;
follow-up = ± 4 weeks.

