4. STUDY DESIGN/TIMELINE/ AND RESEARCH SITES

4.1 Study Design:

To address these questions we will identify opioid addicted prisoners who appear to meet study admission criteria and express interest in XR-NTX treatment, explain the study to them in detail, encourage them to ask questions, and obtain consent from those who remain interested. We will then complete baseline assessments to confirm eligibility (criteria described later) and the first 200 that meet enrollment criteria will be stratified according to male/female and sentenced/not sentenced (e.g. meet/not meet with probation/parole officer), and randomized 1:1 to receive XR-NTX before reentry with the offer of having three additional doses of XR-NTX at NET Steps after reentry, or be given an appointment to be seen at NET Steps same day or up to 7 calendar days after release to receive their first dose of XR-NTX after reentry with the opportunity for 3 additional doses at NET Steps. Follow-ups for participants who have difficulty going to the NETSteps site can have their follow-up injections and assessments done at the [name]. All participants will be assigned a Patient Benefits Manager to help reinstate benefits that were lost during incarceration and all will receive the usual counseling and other services available to NET Steps patients (described later in more detail). A urine drug toxicology screen , adverse events, and an alcohol breathalyzer test will be done weekly and brief assessments will be done at months 1, 2, 4 and 5 with more detailed assessments at months 3 and 6. Criminal justice information on arrests and re-incarcerations will supplement the assessments.

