5 ENROLLMENT AND WITHDRAWAL

5.1 Enrollment

Two hundred (200) prisoners meeting enrollment criteria will be enrolled and stratified according to male/female and sentenced/non-sentenced (e.g. required vs. not required to meet with a probation officer), and randomized to receive XR-NTX before re-entry with follow-up XR-NTX treatment at NET Steps, or randomized to receive their first dose of XR-NTX when they report to NET Steps same day of release up to 30 calendar days post release. Should a prisoner not be released from PPS at the reported release date, and has received his baseline injection of Vivitrol, and the extended incarceration exceeds 30 days, the study will reset his baseline date and administer a 2nd pre-release restart shot prior to the new release date. Additional reset injections may be needed if new release dates are not met. Prisoners will be told that three additional XR-NTX doses will be available at NET Steps and that if they change their mind after reentry they can receive another treatment of their choice. Urine drug tests, adverse events, and a breathalyzer will be done weekly with brief assessments at months 1, 2, 4 and 5, and more detailed assessments at months 3 and 6. PPS data and publicly available criminal justice system information (<http://ujportal.pacourts.us/docketsheets/cp.aspx>) will document rearrests and re-incarcerations. Reasons for screen failure will be recorded; those who relapse will be restarted on XR-NTX or offered the most appropriate treatment at NET Steps or another program of their choice. Efforts will be made to obtain follow-up data on all participants according to the intent to treat design.

5.2 Inclusion criteria:

Opioid dependent with physiological features according to DSM-5; interested in XR-NTX treatment; eligible to have health benefits reinstated; detoxified; age 18 or above; not being transferred to serve a longer sentence in a State or Federal prison; provide their address or phone number along with the names and contact information of

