Randomization will be stratified according to male/female and sentenced/not sentenced (e.g. meet/not meet with probation/parole officer. Those who relapse will be referred to the most appropriate alternative at NET Steps or a program of their choice, or offered XR-NTX if they so choose after completing detoxification and the testing procedures described above to make certain they are free of physiologic dependence before receiving XR-NTX. Follow-up assessments will be done every 4 weeks through month 6, as described above. HIV and hepatitis risk reduction counseling is provided at NET Steps as part of ongoing treatment, as is counseling about the possibility of infections, adverse drug reactions, and overdoses from illicit drug use.

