7. STUDY SCHEDULE OF EVENTS

ASSESSMENT SCHEDULE 7.1 Screening:
	
 - Quiz completed, scored, and reviewed - Informed consent completed and signed - Check of inclusion and exclusion criteria - DSM-5 Checklist - medical/surgical history, including neurological and psychiatric history - physical exam, including a neurological assessment - Vitals- heart rate and blood pressure - height and weight - hematology-Hb,Ht,WBC-diff, platelets* - biochemistry (ALT, AST, ALP, creatinine)* - HCV test, HBV* - HIV test - urine or blood pregnancy test (for women of childbearing potential)
---	--

	
 - Prior/concomitant meds • Drawn by Study if not using historical data - ASI (baseline) - EuroQol - BDI - TLFB - RAB - smoking status

7.2 Baseline/ Enrollment (Week 1)
	
 - Randomization - urine drug tox screen - breathalyzer - urine or blood pregnancy test (for women of childbearing potential) - naloxone challenge* - XR-NTX administered (Day 1)* - recording of AEs/SAEs, if any- Locator Data - Non medical services form - pt satisfaction questionnaire - Check counselling enrollment 
* pre-release or post release

7.3 Week 2 through end of Month 5
	
 - naloxone challenge (at monthly injections/can be clinical observation) - XR-NTX adminis. (mo 2, mo 3, mo 4) - ASI (month 3) - EuroQol (month 3) - BDI (month 3) - urine or blood pregnancy test (monthly) - TLFB (mo 1, mo 2, mo 3, mo 4, mo 5) - RAB (Month 3) - urine drug tox screen (weekly) - alcohol breathalyzer test (weekly) - Non medical services form - record all primary and secondary efficacy in CRF - recording of AEs/SAEs, if any- recording of concomitant medications - check for protocol violations - check time to restoration of benefits - check deaths report -check re-incarceration report - Locator Data

	
 - Check counselling enrollment - End-of-study CRF (if needed) - Pt Remuneration made

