5) Addiction Severity Index (ASI; McLellan, et al, 1992) with items added to the legal section to calculate average number of crimes/day on days when illegal activity occurred (French, Salomé, et al, 2002). This addition estimates criminal activity in the 30 days prior to incarceration and at 12 and 24-weeks by multiplying the number of days of illegal activities by the average number of crimes/day. We will add a question, “Since the last assessment, how many days have you been incarcerated in a facility other than the PPS” to obtain data that is not available in Lock & Track (described below) or the ASI for use in calculating primary and secondary outcomes (e.g., Rajkumar, 1997; French et al, 2002).

6) Urine (UDS) : A Urine Drug toxicology screen will be done at week 1 and thereafter using a urine tox dip stick method. If confirmation or other outside tests are needed by the study, NET Steps will utilize Atlantic

Diagnostic Laboratories (ADL). Atlantic Diagnostic Laboratories (ADL). uses a specialized profile that tests for 14 commonly abused drugs (details in Appendix). All tests performed within PPS will utilize the PPS medical contractors. The lab picks up specimens 5 days/week and results are transmitted electronically to NET Steps or NET@PPS within 24-48 business day hours. Testing costs are reasonable and detailed in the budget justification.

7) Self-Reported Opioid & Other Drug Use: Done using the Time Line Follow-Back (TLFB; Sobel & Sobel, 1992) to assess use of various substances over a specified period of time. For this study it will assess drug and alcohol use over the 30 days prior to incarceration, and during the past 30 days at each monthly assessment.

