13 STATISTICAL HYPOTHESES AND PLAN

13.1 Primary Aims

Before performing analyses, we will apply the following data screening and cleaning procedures: 1) screen for data-entry errors; 2) check for outliers; 3) assess the extent and pattern of missing data, and 4) check that appropriate assumptions of normality are met, as necessary. In all analyses, we will examine whether the assumptions underlying the application of statistical methods have been met, principally through use of standardized residuals, influence diagnostics, and graphical displays. We will check to confirm that the groups do not differ on baseline relevant background variables using analyses of variance (ANOVA) for continuous variables and log-linear models for binary or ordinal responses. The randomization process should minimize the need for inclusion of covariates to reduce bias in treatment comparisons. However, we will consider relevant covariates for inclusion in analyses to improve precision of estimation of treatment effects (Hauck et al. 1998). The statistical procedures that will be used to examine each outcome are listed below.

13.2 Primary Aim 1—Proportion Without Relapse by Month 3:

At each monthly assessment we will determine whether a subject has relapsed based on self-report, physical examination, response to a naloxone challenge, or information from program staff of significant others. Using these data, we will create a binary outcome reflecting whether or not the participant relapsed during the 3 months post-release. We will compare the proportion of participants who relapsed in the two groups using a logistic regression analysis. The analysis will include group as a predictor variable along with all relevant covariates (including the stratification variables). Relapsed will be defined by self-report of 10 or more days in the past 30 days or by two or more opiate positive urine samples in the last 30 days. Positive urine samples will be computed as 5 days of opioid use for each sample. The analysis will be performed using SAS's PROC LOGISTIC.

13.3 Power Analyses for Primary Aim:

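### Follow-up TLFBs look back only 30 days with no catch-up rule, so one missed monthly visit leaves about 26 days of the primary outcome period without a self-reported day count

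*Combined protocol and SAP*

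**What the plan says.** - **Look-back.** Section 8.1 item 7 states that the TLFB is used so that "it will assess drug and alcohol use over the 30 days prior to incarceration, and during the past 30 days at each monthly assessment".
- **Schedule.** Section 7 lists the TLFB at screening, then "TLFB (mo 1, mo 2, mo 3, mo 4, mo 5"), and again at month 6 and at a withdrawal visit. It is not listed at Baseline/Week 1 (7.2), where the first dose appears as "XR-NTX administered (Day 1"), marked as falling before or after release.
- **Spacing.** Section 5.6: "Follow-up assessments will be done every 4 weeks through month 6". The window note under the Study Flow Table gives "monthly = ± 1 week".
- **Outcome.** Section 13.2: "Using these data, we will create a binary outcome reflecting whether or not the participant relapsed during the 3 months post-release". Relapse means at least 10 self-reported days of use in the past 30, or at least two opiate-positive urines in the last 30 days.
- **Scoring.** Section 8.1 item 28 (Relapse CRF) counts each positive urine as 5 days and takes self-reported days from the TLFB.
- **Group B first dose.** Section 4.1 allows "same day or up to 7 calendar days after release", and 5.5 also gives 7 days. Section 5.1 allows "same day of release up to 30 calendar days post release".

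**The concern.** The outcome covers the whole of the first three months, but each TLFB sees only the 30 days before the visit at which it is given. If a monthly visit is missed, the next TLFB does not reach back over the missed month, and no section says how that month is to be scored. Someone who used heavily soon after release, missed early visits and was abstinent before month 3 could attend month 3 and be scored as not relapsed.

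Section 13.3 itself says that relapse to opioids usually comes within days or weeks, and for released prisoners often almost at once. The early period is therefore where a missing day count could cost most.

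A second question concerns Group B, whose first dose follows release. If the month-1 visit is timed from that dose, its 30-day look-back may not reach the release date.

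**Working it through.** **The plan's own figure.** Section 13.3 states 80% power. With 10% attrition, n = 100 × 0.9 = 90 per arm. At two-sided 0.05, 50% v 30% (OR 2.33) gives 78.7%, and 50% v 29.4% (OR 2.4) gives 81.1%. The stated power is reproduced. Nothing below changes the sample size; the question is what the outcome captures.

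**Inputs.** Look-back 30 days (8.1 item 7); visits every 28 days (5.6); window ±7 days (Study Flow Table); Group B interval from release to first dose g = up to 7 days (4.1, 5.5) or up to 30 days (5.1).

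**Between two completed TLFBs.** Uncounted days = max(0, days between them − 30). The low and high columns place the two visits at opposite window extremes.

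| Visits missed between them | Interval: low / on time / high | Uncounted: low / on time / high |
|---|---|---|
| 0 | 14 / 28 / 42 | 0 / 0 / 12 |
| 1 | 42 / 56 / 70 | 12 / 26 / 40 |
| 2 | 70 / 84 / 98 | 40 / 54 / 68 |

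If a month is taken as 30 days, one missed visit leaves 30 uncounted days (16 to 44).

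**From release, with visits timed from release.** Release is a fixed date, so only the visit end moves.
- Month 1 missed, month 2 at day 56: 56 − 30 = 26 uncounted days (49 − 30 = 19 to 63 − 30 = 33).
- Months 1 and 2 missed, month 3 at day 84: 84 − 30 = 54, and 54/84 = 64%.
- Month 3 missed, month 4 at day 112: this TLFB reaches back to day 82, so days 56 to 82 (26 days) have no count.

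**Group B interval before first dose, month-1 TLFB attended.**
- *Month 1 timed from first dose.* The visit falls on day g + 28 after release and reaches back to day g + 28 − 30 = g − 2. For g = 7, 5 days are uncounted; for g = 30, 28 days. One week early: 0 of 7 or 21 of 30. One week late: the whole interval.
- *Month 1 timed from release.* The visit on day 28 reaches past the release date, so nothing is lost for either value of g. On day 35, the first 35 − 30 = 5 days are lost.

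For Group A, dosed before release, an on-time month-1 TLFB covers the release date on either clock.

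**What the other sources add.**
- *Risk Assessment Battery (RAB, 8.1 item 14).* It asks about frequency of substance use over 12 weeks, at weeks 12 and 24. An on-time week-12 RAB timed from release covers all 84 days. Timed from first dose, it starts at that dose and misses the earlier interval. If month 3 is missed, the week-24 RAB reaches back only to day 168 − 84 = 84. Neither 13.2 nor item 28 names the RAB, and nothing shows that it can place 10 days within a 30-day period.
- *Drug use history before the first naloxone challenge (10.1.3).* In Group B this is taken after release. No look-back or day count is specified.
- *Follow-up Questionnaire (5.9.2.1; 8.1 item 29).* It seeks relapse information in person or by telephone. Its look-back is not given, nor any link to the 10-day rule.
- *Weekly urines.* Two positives in 30 days are enough for relapse, but only if the participant attends.
- *Repeat-urine rule (5.5).* A second opioid-positive test at the first-dose stage counts as relapse. It does not count use that had stopped by then.

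**The case against.** A reader might infer that drug use in a missed month, or in Group B before the first dose, is never asked about. The documents do not support that. The RAB, the drug use history, the Follow-up Questionnaire and the repeat-urine rule all reach some of this time. In the example of missing months 1 and 2, the RAB is due at the very visit attended. What is missing is a day count usable in the relapse rule.

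A reader might also infer a certain bias between the arms, because only Group B has an interval between release and first dose. That depends on the clock. Section 7.2 ties Day 1 to the first dose, but 13.2 defines the outcome from release and 8.1 items 13 and 19 time assessments from reentry. On a release clock, an on-time month-1 TLFB covers the interval. The 28-day figure also needs the 30-day limit in 5.1, against 7 days in 4.1 and 5.5. With 7 days the hole is 5 days, which cannot meet the 10-day rule alone, though it could tip a count. Missed visits can occur in both arms, and the documents give no basis for estimating how many participants would be misclassified.

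Other points in the plan's favour stand. Section 13.2 also lists physical examination, naloxone response and information from staff or significant others. Section 9 alerts investigators to missed assessments, and 13.5 models dropout, so missed visits are visible. The 12-day hole with no missed visit needs consecutive visits at opposite window extremes. None of this supplies a count for the missed month or a rule for scoring it.

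**Conclusion.** The concern holds in a limited form. The follow-up TLFB has a fixed 30-day look-back and no catch-up rule, and it is the only named source of the self-reported days used to score relapse. One missed visit leaves about 26 days (12 to 40) without that count; two missed visits before day 84 leave 54 of 84 days. These figures assume 28-day spacing and the ±7-day window.

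The Group B element is conditional. An on-time month-1 TLFB misses 5 of 7 or 28 of 30 days if visits run from first dose, and none if they run from release. The unsettled clock and the two limits need reconciling in their own right.

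This should be fixed as a cheap improvement. It does not show that the primary comparison is biased in a known direction, and it changes no sample-size figure.

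**What to change.** 1. In 8.1 item 7 and on the TLFB form, make the follow-up look-back run from the last completed TLFB and, for the first TLFB after release, from the release date, in both arms. Section 8.1 already frames the EuroQol (item 12), the Non-Study Medical Services form (item 20) and an added ASI question (item 5) by reference to the preceding assessment.
2. In 13.2, apply the 10-day/two-urine rule to any 30-day period between release and month 3 that these data cover, not only to the 30 days before an attended visit. Fix this derivation before outcome data are analysed.
3. State whether visit months run from release or from first dose (7.2 against 8.1 items 13 and 19, and 13.2), and reconcile the Group B limit (4.1 and 5.5 against 5.1).

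**Cost.** A few more minutes and longer recall for participants who missed visits, with the recall error that brings; a revised form instruction; and new derivation code. Item 2 is more than a wording change, because it alters how the primary endpoint is computed, and it should be documented as such.

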Candidates who complete all inclusion procedures will be randomized into two groups; group A who will be scheduled to return to the research office prior to re-entry for a drug test, a breathalyzer test, another pregnancy test (females), and naloxone challenge, and group B who will be scheduled to for a drug test and naloxone challenge after release within 7 days at the NET treatment clinic. Those with a opioid positive drug test will be asked to return in 3 days for a repeat test; failure to have an opioid negative test on the second occasion will count as a relapse. Patients who fall into this category will be referred for other treatment or can be restarted on study medication if they are detoxed and elect to continue. These patients will continued to be followed for their weekly and monthly assessments. Those in group A or B with an opioid negative drug test and who pass the naloxone challenge will receive their first dose of XR-NTX with continuing XR-NTX for 3 months thereafter at NET Steps.. A benefits manager will schedule an appointment with the participant after they have met the inclusion criteria, have been randomized, and have a valid release date. Those who change their mind about XR-NTX will be eligible for methadone, buprenorphine-naloxone, intensive outpatient treatment without medication, or referral to another program if they so choose. If a subject in Group A, who received an injection before release from PPS is held over in PPS pass the expected release date by 30 days but not greater than 6 months, the subject will not be given a second injection inside the prison. The subject will be considered in the study but not injected until the new established release date for his next injection. The injection visit dates will be reset to begin as his first injection, with the next injection post release.

If a subject in Group A, who received an injection before release from PPS is held over in PPS more than the expected release date but less than or equal to 30 days from his first injection, the subject’s next injection will be considered his 2nd injection and his visit schedule will not change.

Table 1: Study Interventions and Assessments Flow Chart

	Months 1-3	Month 6
--	-------------------	----------------

XR-NTX Before Reentry (N=100)	XR-NTX + Therapy + Follow Up	Therapy + Follow Up
XR-NTX After Reentry (N = 100)	XR-NTX + Therapy + Follow Up	Therapy + Follow Up

5.6 Randomization Procedures:

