8) Naloxone challenge: A baseline COWS is administered prior to the naloxone challenge by administering 0.4 to 0.8 mg of naloxone I.M. and observing the patient for 15 - 30 minutes to establish absence of physiological dependence (score of <5 on the COWS). A second COWS is administered after the naloxone challenge is given and the patient is also observed for 15 – 30 minutes. The naloxone challenge is done prior to subsequent XR-NTX doses unless it is clear that there has been no relapse, or that relapse has occurred, in which case it will not be done. Determination presence/absence of relapse is a clinical evaluation based on self-report, urine test results, reports from significant others (if available), and physical examination (rhinorrhea, lacrimation, fresh tracks or puncture marks). If withdrawal occurs after a naloxone challenge, clonidine 0.2 to 0.6 mg will be administered to suppress it and the participant will be observed with blood pressure checks every 15 minutes until symptoms subside and there is no evidence of clonidine-induced hypotension.

9) Relapse to Opioid Dependence with Physiological Features: Determined from self-report, physical assessment, urine tests, reports from significant others if available, and/or a positive naloxone challenge in cases where it is administered prior to a XR-NTX.

10) Time to Relapse: Determined by time between absence of physiologic dependence and time that relapse occurred, and documented using methods described above.

11) Weeks in Addiction Treatment: Data obtained from NET Steps clinical records, patient self-report, and verification from other treatment provider (for those reporting treatment elsewhere). A week will be counted as beginning on Monday and ending the following Sunday. Having 5 or more days of protected time from a previous XR-NTX injection, or receiving 5 or more days of methadone or buprenorphine-naloxone, or having a counseling appointment lasting 30 minutes or more will be counted as a week in treatment.

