XR-NTX will precipitate or exacerbate opioid withdrawal unless the patient has been opioid-free for 7-10 days, which is expected to be the case in all but a very few potential study candidates. An opioid negative urine test, drug use history, psychiatric interview and observation for signs and symptoms of current opioid use or withdrawal will be done prior to the first naloxone challenge and the challenge will not be done unless the person appears to be free of physiologic opioid dependence. The absence of current physiologic dependence will be confirmed by self-report, clinical observations, and a score of <5 on a COWS that is administered 15 -30 minutes after receiving 0.4 - 0.8 mg naloxone I.M. Clonidine 0.2 to 0.6 mg will be used to suppress withdrawal if it occurs, and blood pressure will be checked every 15 minutes until there is no evidence of hypotension and/or withdrawal over the next 45-60 minutes. Similar procedures will be followed prior to subsequent XR-NTX injections, however the naloxone challenge will not be re-administered if the clinical situation clearly indicates the absence of relapse. Patients that have relapsed will be referred to the most appropriate available treatment, as previously described.

10.1.4 Opioid Overdose From an Attempt to Overcome Opioid Blockade: Patients will be told that attempting to overcome the XR-NTX blockade by administering large amounts of opioids is dangerous and may result in fatal overdose.

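### Time to relapse has no dated time origin; dated by the naloxone challenge, the clock would start before release in Group A and after release in Group B

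*Combined protocol and SAP*

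**What the plan says.** - **Definition.** Section 8.1 item 10 gives time to relapse as "Determined by time between absence of physiologic dependence and time that relapse occurred", documented by the methods listed before it. It names no date, visit or procedure as day 0. Section 13.4 assigns the outcome to a Cox model and mentions covariates and software, but no origin.
- **How the state is established.** Item 8 of the same section describes the naloxone challenge as done "to establish absence of physiological dependence (score of <5 on the COWS" being the criterion). Section 10.1.3 says: "The absence of current physiologic dependence will be confirmed by self-report, clinical observations, and a score of <5 on a COWS", the scale being scored after naloxone.
- **When the challenge happens.** Section 5.5 describes "group A who will be scheduled to return to the research office prior to re-entry for a drug test" and the challenge, while Group B is scheduled for a "drug test and naloxone challenge after release within 7 days at the NET treatment clinic". The baseline row of section 7 stars both the challenge and the first injection, with the footnote "pre-release or post release".
- **Relapse at that visit.** For a participant with an opioid-positive test, section 5.5 adds that "failure to have an opioid negative test on the second occasion will count as a relapse". Such a participant may later be detoxified and restarted.
- **Other anchors.** Section 13.2 counts the primary outcome over the 3 months after release. Section 5.2 requires participants in both arms to be detoxified at entry. Section 13.5 includes everyone randomised.

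**The concern.** A time-to-event analysis needs one time zero with the same meaning in both arms. Item 10 supplies a state, so the date must be chosen when the analysis is programmed, in a trial that section 16.2 says is not double blinded.

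The challenge is a natural choice because item 8 describes its purpose in almost the same terms. It would, however, tie the origin to the randomised arm. Group A would be credited with days in custody before release. Group B would lose its first days in the community, when section 2.3 says relapse often occurs. A Group B participant who relapses before passing a challenge would have an event with no start, or a start after the event if later restarted. The plan keeps all randomised participants but does not say how such a person enters the Cox model.

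**Working it through.** **The plan's own figure.** The documents give no power, event count or hazard ratio for time to relapse. The nearest figure is the primary-outcome power in section 13.3: 80% for about 20 points, 50% relapse in controls, 100 per group less 10% attrition. With 90 per arm, 50% against 30% gives 78.7% (arcsine method, h = 0.4115: 78.8%). Taking OR 2.4 literally, odds of 1/2.4 give 29.4% relapse and 81.1% power. The figure is reproduced, and the time origin does not enter it.

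**Inputs for the time-to-relapse check**

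- From the documents: 100 per arm; 50% of Group B relapsed by 3 months (taken as day 90); 6 months of follow-up (taken as 180 days after release); two-sided 0.05.
- Group B first visit: up to 7 days after release (sections 4.1 and 5.5) or up to 30 (section 5.1). Both were run.
- Assumed: the Group A interval from challenge to release, which the documents do not give. It was drawn uniformly from 0-7 or 0-30 days. The upper value is not arbitrary: section 5.5 foresees Group A being held up to 30 days from first injection with the visit schedule unchanged.
- Also assumed: uniform visit times, no relapse in custody, no attrition.

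**Model.** Time from release to relapse has S(t) = exp(-λ(t/90)^k), with λ = -ln(1 - p), where p is the proportion relapsed by day 90. The shape is k = 1 (constant hazard) or k = 0.6 (front-loaded). With p = 0.5, λ = 0.693. The true HR is ln(1 - pA)/ln(1 - pB): 1.00 for 50% against 50%; ln 0.6/ln 0.5 = 0.74 for 40% against 50%; ln 0.7/ln 0.5 = 0.51 for 30% against 50%. Under the challenge origin, Group A times gain the lead and Group B times lose the visit delay.

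**Group B relapses before the visit.** For k = 1 and a visit uniform on 0 to w days, the proportion is 1 - (1 - e^(-a))/a with a = 0.693w/90. For w = 7, a = 0.054 and the result is 2.6 per 100. For w = 30, a = 0.231 and the result is 10.7 per 100. With k = 0.6 the figures are 8.9 and 19.9.

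**No true effect, challenge origin** (HR below 1 favours Group A; ranges cover both shapes)

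| Group A lead / Group B visit (days) | Early Group B relapses kept: HR | Rejection | Dropped, k = 0.6: HR |
|---|---|---|---|
| 0-7 / 0-7 | 0.93-0.94 | 6.7-7.2% | 1.08 |
| 0-30 / 0-7 | 0.83-0.86 | 14-21% | 0.98 |
| 0-7 / 0-30 | 0.84-0.88 | 11-20% | 1.22 |
| 0-30 / 0-30 | 0.74-0.80 | 24-43% | 1.10 |

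Where kept, these relapses were placed at time zero or timed from release; the two choices agree within 0.01. Dropping them with k = 1 gives 0.85-0.97. Over repeated simulations the dropped range is 0.85 to 1.24. Values above 1 arise because Group B then restarts its clock after its own high-hazard period. With release as the origin in both arms, HR is 1.00 and rejection 4.6-5.4%.

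**With a true effect, early relapses kept.** A true HR of 0.51 is estimated at 0.48-0.49 (both gaps 0-7) or 0.40-0.43 (both 0-30). A true HR of 0.74 is estimated at 0.69-0.70 or 0.56-0.60, and rejection rises from 37-44% under the release origin to 49-58% or 78-92%.

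**Detoxification origin.** The same lead of up to 180 days in both arms gives 0.52-0.53 where the truth is 0.51, with power about 2 points lower.

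**The case against.** The best defence is that the challenge confirms a state that already exists. Participants are detoxified at entry. Section 10.1.3 withholds the challenge unless the person already appears free of dependence. The rule in section 5.5 that a second positive test counts as relapse before any challenge has been passed presupposes that absence of dependence was established earlier. Item 10 refers to methods in the plural, and items 13 and 19 of section 8.1 time assessments from re-entry. On this reading the origin is similar in both arms and almost nothing is lost.

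This stands in part. The documents do not fix the challenge as the origin. They do not fix detoxification either, and it has no defined date, so the gap remains on both readings.

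Two further objections stand in full. The larger biases need a Group A lead that the documents do not give, and the largest also needs the 30-day Group B window, which two other sections contradict. And the study schematic, flow table and appendix schedule cannot be read in the available text, so an origin shown only there cannot be ruled out.

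A reader might infer that the planned Cox analysis always favours Group A. The documents do not support that: the direction is fixed only if pre-challenge Group B relapses are kept, and a literal challenge origin gives those people no valid time.

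**Conclusion.** The missing date is established as far as the readable text goes, and it should be fixed. The bias is conditional on using the challenge as the origin. In that case the null HR ranges from about 0.93 (both gaps within a week) to 0.74-0.80 (both up to a month) with early Group B relapses kept, and is about 0.85-1.24 with them dropped. These figures rest on the assumed gaps and hazard shapes and ignore attrition. With everyone kept, the direction at the planned effect does not change and the benefit is exaggerated; the conclusion is most exposed if the true effect is smaller than planned. If detoxification dates the state, the effect is nearly nil.

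It would be wrong to carry this over to the main result. The primary outcome is anchored to release, and neither it nor its stated power is affected. This is one of ten secondary outcomes.

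**What to change.** In section 8.1 item 10 and section 13.4, define time to relapse in both arms as days from actual release from PPS (the Lock & Track release date) to first relapse after release. This is the anchor of the primary outcome. Then state that:

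- Group B relapses before the challenge or first dose are timed from release and never dropped;
- positive tests in custody are reported by arm and not scored as day-0 events, because only Group A has that test in custody;
- participants never released are reported by arm;
- a sensitivity analysis takes randomisation as time zero and includes everyone randomised.

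Release is the better main origin. If the never-released share is 5% in one arm and 10% in the other, with no true effect, the randomisation origin gives HR 0.91-1.09 and 6.6-9.1% rejection. With equal shares of 5-10%, both origins give 0.99-1.00.

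The sponsor must also reconcile the Group B first-visit window (sections 4.1 and 5.5 against 5.1) and the Group A holdover text (section 5.1 against 5.5). This point takes no position on either.

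The cost is a few sentences and one sensitivity analysis, with no new data: Lock & Track holds release fields and randomisation is a scheduled study step. The small downside is that never-released participants fall outside the main time-to-relapse analysis.
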